Study size and power: All individuals who meet the eligibility criteria during the study period in the VHA database will be included. The sample size achieved will depend on the number of individuals administered ABRYSVO identified within the VHA database during the study period, which will increase over time. Data will be analyzed at two different time points to add newly vaccinated individuals and index-matched controls. Analyses using the primary internal comparator cohort design will have sufficient power (80.0%) to detect a 2-fold and 1.5-fold increased risk of safety events associated with ABRYSVO assuming a baseline rate of 33.9 events per 1,000 person-year and 4:1 matching ratio of controls to ABRYSVO vaccinees with a sample size of 37,444 and 116,493 individuals at least 60 years of age vaccinated with ABRYSVO, respectively. For individuals 18-59 years of age, based on an expected background rate of 4.4 per 1,000 person-years for incident atrial fibrillation and assuming the same matching rate of controls to ABRYSVO vaccinated individuals (ie, 4:1 ratio), a sample size of 286,730 and 892,049 individuals vaccinated with ABRYSVO is needed to detect a 2-fold and 1.5-fold increase in the incidence rate ratio (IRR), respectively with a power of 80% and a one-sided alpha level of 0.05.

Data analysis: All analyses will be conducted separately among individuals at least 60 years of age and older and among individuals 18-59 years of age. Pooled analyses among individuals 18 years of age or older may be conducted using combined individual-level data from both age groups. If heterogeneity in patient characteristics (other than age) is not observed and characteristics are considered to be sufficiently similar, then individual-level data from both age groups will be combined, and the descriptive analyses of characteristics and outcomes will be conducted using the combined dataset. If sample size is sufficient to allow comparative cohort analyses to be performed separately among individuals 18-59 years of age and individuals 60 years and older, then comparative analyses will also be performed in the pooled population.

Baseline demographics and clinical characteristics for individuals administered ABRYSVO and contemporary vaccinated or unvaccinated controls will be summarized using descriptive statistics. Descriptive statistics will also be used to summarize vaccination patterns for ABRYSVO.

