9.5.1. Power

The study population will consist of VHA enrollees 18 years of age and older without a prior history of atrial fibrillation as assessed during a 2-year baseline period. Analysis will be conducted separately among individuals at least 60 years of age and among individuals 18-59 years of age.

Of the nine million VHA enrollees,²⁰ it is estimated that 56% are at least 60 years of age⁵⁹ and one million VHA enrollees have a prior history of atrial fibrillation.⁶⁰ Based on previous studies using VHA data, it is further estimated that 85% of the eligible population will have continuous enrollment during a 2-year baseline period.⁶¹ This results in approximately 3.8 million VHA enrollees at least 60 years of age estimated as eligible for inclusion in the study. Separately, approximately 11% of adults aged 18 to 49 and 29% of those aged 50 to 64 are immunocompromised or have a chronic condition that puts them at risk for severe RSV disease.⁶² As such, an estimated 330,000 to 868,000 VHA enrollees aged 18 to 59 may be eligible for inclusion in the study.

Table 2 illustrates the estimated sample size required for the weighted Cox regression using the internal comparator cohort design for individuals at least 60 years of age and for individuals 18-59 years of age, separately. For individuals at least 60 years of age, based on an expected background rate of 33.9 per 1,000 person-years for incident atrial fibrillation reported for male Medicare beneficiaries 65 years of age and older, assuming controls (vaccinated or unvaccinated) will be matched to ABRYSVO vaccinated individuals on a 4:1 ratio, a sample size of 37,444 and 116,493 individuals vaccinated with ABRYSVO is needed to detect a 2-fold and 1.5-fold increase in the IRR with a power of 80% and a one-sided alpha level of 0.05, respectively. For individuals 18-59 years of age, based on an expected

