The power calculations are based on assuming one-sided α =0.05, a power of 80%, and a risk interval of 4 days corresponding to the 0-3 day risk interval. A background rate of 33.9 incident atrial fibrillation events per 1,000 person years as observed among male Medicare beneficiaries 65 years of age and older was used for individuals at least 60 years of age, and a background rate of 4.4 incident atrial fibrillation events per 1,000 person years as observed among male 45-54 years of age was used for individuals 18-59 years of age.

Table 3 illustrates the estimated sample size required for the conditional Poisson regression using the SCRI design for individuals at least 60 years of age and for individuals 18-59 years of age, separately. For individuals at least 60 years of age, based on the expected background rate of 33.9 per 1,000 person-years for incident atrial fibrillation reported for male Medicare beneficiaries 65 years of age and older and a 4-day risk window (ie, days 0-3), a sample size of size of 38,453 and 129,204 individuals vaccinated with ABRYSVO is needed to detect a RR of 2 and 1.5, respectively, with 80% power and a one-sided alpha level of 0.05. ⁶⁶ For individuals 18-59 years of age, based on an expected background rate of 4.4 per 1,000 person-years for incident atrial fibrillation reported for male 45-54 years of age ⁶⁴ (which is assumed to comprise the majority of the 18-59 years age group) and a 4-day risk window (ie, days 0-3), a sample size of size of 294,458 and 989,381 individuals vaccinated with ABRYSVO is needed to detect a RR of 2 and 1.5, respectively, with 80% power and a one-sided alpha level of 0.05. ⁶⁶

Table 3. Sample size calculations for the conditional Poisson regression using the SCRI design

RR	Total number of events needed	Number of events expected in control interval	Number of ABRYSVO vaccinated individuals needed (N)	
Individuals at	Individuals at least 60 years of age			
Days 0-3 risk	interval			
1.2	787	467	718,310	
1.5	156	84	129,204	
2.0	53	25	38,453	
3.0	22	9	13,843	
Days 0-1 risk interval			,	
1.2	1,025	764	1,175,137	
1.5	197	138	212,263	

Table 3. Sample size calculations for the conditional Poisson regression using the SCRI design

RR	Total number of events needed	Number of events expected in control interval	Number of ABRYSVO vaccinated individuals needed (N)	
2.0	64	41	63,064	
3.0	24	13	19,996	
Days 0-30 risk	interval		,	
1.2	747	340	118,089	
1.5	153	62	21,534	
2.0	54	18	6,252	

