9.7.2.2. Comparison with Contemporary Controls

Average treatment effect among the treated (ATT) weighting will be used to ensure baseline comparability between the ABRYSVO vaccinated cohort vs. contemporary vaccinated control cohort and between the ABRYSVO vaccinated cohort vs. contemporary unvaccinated control cohort. ATT weighting creates a "pseudo-population" in which the distribution of covariates is, on average, the same in each cohort. ⁶⁸ Specifically, ATT weights will be calculated to allow for estimation of the average treatment effect among individuals receiving ABRYSVO.⁶⁹ This approach will be taken to ensure that inference from the analysis will be applicable to this population. Individuals receiving ABRYSVO will receive an ATT weight of one. Individuals not receiving ABRYSVO will receive an ATT weight equal to the odds of receiving ABRYSVO conditional on their demographic and clinical characteristics as of the index date, which will be calculated based on the propensity score (PS). The PS is defined as an individual's probability of receiving ABRYSVO, conditional on observed baseline covariates, and will be calculated using a logistic regression model. The logistic regression model will include the cohort variable (ie, ABRYSVO vs. vaccinated or unvaccinated control) as the dependent variable, and the independent variables will include variables deemed clinically important and baseline covariates that have standardized differences ≥10% between the two cohorts. Specifically, ATT weights will be PS/(1-PS) for individuals with no record of ABRYSVO. The distribution of weights will be examined to assess extreme values, and truncation will be considered if necessary.

Weighted Cox regression with robust standard errors to account for within-subject correlation will be conducted to compare the risk of safety events between cohorts. Hazard ratios and corresponding 95% CIs will be summarized.

9.7.2.3. SCRI Design using the Conditional Poisson Regression for Comparison to Post-vaccination Control Intervals

SCRI design with post-vaccination control time period will include cases (ie, individuals vaccinated with ABRYSVO who experience safety events following vaccination) who have at least 41 days (or 38 days or 91 days for secondary analysis) of enrollment post-index to compare the incidence of safety events occurring in the risk interval following vaccination with the incidence of safety events occurring during the post-vaccination control interval.

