A conditional Poisson regression model will be used to compare the rates of safety events in the risk interval vs post-vaccination control time period. From this model, we will report rate ratios and 95% CIs that will be interpretated as the relative incidence for the safety event in the risk interval compared to the control interval.

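### Sample sizes assume a one-sided 0.05 level, but results are reported only with 95% CIs and nothing links the two; at the stated N the SCRI interval has about 71% power, not 80%

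*Protocol*

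**What the plan says.** Section 9.5.1 states for the 60+ group that a sample of 37,444 and 116,493 ABRYSVO recipients, respectively, "is needed to detect a 2-fold and 1.5-fold increase in the IRR with a power of 80% and a one-sided alpha level of 0.05". The note to Table 2 repeats this: "The power calculations are based on assuming one-sided α =0.05, a power of 80%, and a risk interval of 4 days". The text and note for Table 3 (SCRI design) use the same level and power.

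For the cohort comparison, section 9.7.2.2 plans an ATT-weighted Cox model with robust standard errors and says "Hazard ratios and corresponding 95% CIs will be summarized". For the SCRI comparison, section 9.7.2.3 says "we will report rate ratios and 95% CIs". Section 9.7 contains no one-sided test, 90% CI or one-sided bound. Section 9.7.2.5 starts a risk-factor analysis if an increased risk is observed, without saying what counts as observed.

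The Abstract claims that the primary design "will have sufficient power (80.0%) to detect a 2-fold and 1.5-fold increased risk of safety events" in the 60+ group and gives no alpha level in that sentence. The level appears only in the following sentence, on the 18-59 group.

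**The concern.** A conventional 95% CI excludes 1 from below at one-sided 0.025, which is stricter than the level used for sizing. If readers judge increased risk by that interval, the only inferential output planned, the quoted 80% belongs to a different criterion.

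This has operational weight. Section 9.5.1 holds back the comparative analyses until enough atrial fibrillation events have been seen for adequate power, and provides for contingency talks with the FDA about reaching the target sample size. That target depends on the alpha level. In a post-marketing safety commitment, a 95% CI that includes 1 could also be read as reassurance with less power behind it than stated.

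**Working it through.** **Inputs (section 9.5.1 and its tables).** "expected background rate of 33.9 per 1,000 person-years for incident atrial fibrillation" in the 60+ group and 4.4 per 1,000 in the 18-59 group; a 4-day risk interval; controls that "will be matched to ABRYSVO vaccinated individuals on a 4:1 ratio"; one-sided 0.05; power 80%. Normal quantiles: 1.645 (one-sided 0.05), 1.960 (one-sided 0.025), 0.842 (80% power).

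**1. Reproducing Table 2.** The 60+ cells match an unpooled Wald formula for a difference of two Poisson rates:

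n = (z_α + z_β)² × (λ₁ + λ₀/k) / (λ₁ − λ₀)², with k = 4.

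- λ₀ = 0.0339 × 4/365 = 0.00037151. For IRR 2.0, λ₁ = 0.00074301.
- n = 6.1826 × 0.00083589 / (0.00037151)² = 37,444, as printed.
- IRR 1.5 gives 116,493, as printed. The 18-59 cells agree within 0.7%.

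The printed N are therefore truly one-sided 0.05 figures.

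**2. Same formula at one-sided 0.025.**

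- Power at the stated N = Φ(1.645 + 0.842 − 1.960) = Φ(0.527) = 70.1% (69.8% in the 18-59 cells checked).
- N factor for 80% = (1.960 + 0.842)² / (1.645 + 0.842)² = 1.2695.
- 60+: 37,444 becomes about 47,536, and 116,493 about 147,890.
- 18-59: scaling the printed values gives about 364,009 and 1,132,474. Rerunning the formula gives 366,244 and 1,139,426.

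**3. The hazard-ratio scale.** Table 2 rests on a rate difference, but the planned estimate is a ratio. With more controls than recipients, the difference formula is conservative for a ratio. At N = 37,444 and IRR 2.0 the expected events are 37,444 × 0.00074301 = 27.8 in recipients and 4 × 37,444 × 0.00037151 = 55.6 in controls.

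- Log-ratio Wald approximation: ln 2 / √(1/27.8 + 1/55.6) = 2.98, so power = Φ(2.98 − 1.96) ≈ 85%. For IRR 1.5 (64.9 and 173.1 events) it is about 80%.
- Poisson simulation of the log rate ratio, 400,000 runs per cell, no weighting, share with the 95% CI lower limit above 1:

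| Group, IRR (4:1) | Stated N | Protocol formula, one-sided 0.025 | Ratio CI, unweighted |
|---|---|---|---|
| 60+, 2.0 | 37,444 | 70.1% | 81% |
| 60+, 1.5 | 116,493 | 70.1% | 77% |
| 18-59, 2.0 | 286,730 | 69.8% | 81% |
| 18-59, 1.5 | 892,049 | 69.8% | 77% |

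At the 2:1 ratio, also in Table 2, the unweighted 60+ figures are 77% (IRR 2.0) and 74% (IRR 1.5).

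**4. ATT weighting.** Table 2 makes no allowance for weighting, and the protocol gives no variance inflation. Treating the inflation as an assumption, the log-ratio approximation (60+, 4:1) gives:

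| Assumed variance inflation | IRR 2.0 | IRR 1.5 |
|---|---|---|
| 1.00 | 85% | 80% |
| 1.10 | 81% | 76% |
| 1.25 | 76% | 70% |
| 1.50 | 68% | 62% |

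This approximation runs about 2 to 4 points above the simulation at inflation 1.00, so the table is slightly optimistic.

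**5. SCRI design.** With r = 4/11 (4-day risk, 7-day control interval), the signed-root method uses

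A = 2[(Rr/(Rr+1−r)) ln R − ln(Rr+1−r)], B = ((ln R)²/A) × Rr(1−r)/(Rr+1−r)², events = (z_α + z_β√B)²/A.

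- RR 2.0: A = 0.1190, B = 1.0045. Events = 52.0 at one-sided 0.05 (Table 3 prints 53) and 66.0 at one-sided 0.025.
- RR 1.2, 1.5 and 3.0 give 783.9, 154.8 and 20.6, against 787, 156 and 22 printed.
- Power at 53 events = Φ((√(53 × 0.1190) − 1.960)/√1.0045) = Φ(0.551) = 70.9%. At 156 events for RR 1.5 it is 70.5%. At one-sided 0.05 the same counts give 80.7% and 80.3%.

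**The case against.** The strongest reply is that the protocol contains no false arithmetic. The level is disclosed, the N reproduce, and 80% is correct for the one-sided test assumed. The comparative question is directional and secondary to estimating incidence. A one-sided 0.05 test can sit beside descriptive 95% CIs, and the signal criterion may be in an SAP that is not shown. All eligible recipients are included, so the stated N is not a recruitment cap, and the gate on the comparative analyses is worded in events. The one-sided level also appears in the Abstract's next sentence.

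Most of this stands. That the 95% CI will serve as the decision tool is an inference, since no section makes exclusion of 1 the rule. But the protocol itself fixes both the sizing level and the interval level and plans no one-sided test, so the missing link is not only a matter of SAP detail.

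A reader might go further and infer that the primary cohort analysis has only 70% power for its reported interval, or that it needs 27% more recipients. The documents do not support that. Both figures follow from the rate-difference formula behind Table 2, whereas section 9.7.2.2 reports hazard ratios, for which unweighted power at the stated N is about 81% (2-fold) and 77% (1.5-fold).

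**Conclusion.** The mismatch is real and unreconciled in the protocol. Its size depends on the design.

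- **SCRI:** about 71% power for the reported 95% CI at RR 2.0 and 1.5, against 80% stated. This applies directly to the interval that will be reported.
- **Cohort, protocol's own formula:** 70% at one-sided 0.025, or N larger by 27%.
- **Cohort, hazard-ratio CI (4:1):** about 81% for a 2-fold and 77% for a 1.5-fold increase without weighting, and less after ATT weighting by an unstated amount. Before weighting, the 2-fold target is met and the 1.5-fold target falls about 3 points short.

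These figures assume that the 95% CIs are two-sided, that the background rates and 4-day window are as stated, and that event counts are Poisson.

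**What to change.** Choose one of two routes.

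1. State in sections 9.5.1 and 9.7 that the signal criterion is the lower limit of the two-sided 90% CI (a one-sided 95% bound), and report it beside the 95% CI. The present alpha level then stands.
2. Restate power and N in section 9.5.1, Tables 2 and 3 and the Abstract at one-sided 0.025, using a calculation for the ratio analyses actually planned and, for the cohort design, a stated allowance for ATT weighting.

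Under either route, put the alpha level beside the 80.0% figure for the 60+ group in the Abstract. The cost is protocol wording and, for the second route, recalculated tables. The design does not change and no additional enrolment is required.

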background rate of 4.4 per 1,000 person-years for incident atrial fibrillation reported for males 45-54 years of age⁶⁴ (which is assumed to comprise the majority of the 18-59 years age group as the VHA population is generally older) and assuming the same matching rate of controls to ABRYSVO vaccinated individuals (ie, 4:1 ratio), a sample size of 286,730 and 892,049 individuals vaccinated with ABRYSVO is needed to detect a 2-fold and 1.5-fold increase in the IRR, respectively, with a power of 80% and a one-sided alpha level of 0.05.63 Power of $\geq 80\%$ is typically desirable in drug safety research and the FDA views a risk ratio (RR) of >3 as meaningful, so these have also been used for the power calculations. The secondary objective's comparative analyses will only be conducted when a sufficient number of atrial fibrillation events have been observed for the analyses to be adequately powered.

Vaccine uptake will be monitored during the course of the study. If a sufficient number of atrial fibrillation events are not observed by the end of the planned study period, Pfizer will discuss contingency plans with the FDA to achieve the target sample size.

Table 2. Sample Size Calculations for the Weighted Cox Regression Using the Internal Comparator Cohort Design

Matching ratio (controls: ABRYSVO vaccinated)	IRR	Number of controls needed in each comparator cohort (N)	Number of ABRYSVO vaccinated individuals needed (N)
Individuals at leas	t 60 years of age		
4:1	1.2	2,413,066	603,267
	1.5	465,972	116,493
	2.0	149,777	37,444
	3.0	54,086	13,522
2:1	1.2	1,414,556	707,278
	1.5	266,270	133,135
	2.0	83,210	41,605
	3.0	29,124	14,562
Individuals 18-59	years of age		,
4:1	1.2	18,478,144	4,619,536
	1.5	3,568,194	892,049
	2.0	1,146,920	286,730
	3.0	414,166	103,542
2:1	1.2	10,832,015	5,416,008
	1.5	2,038,968	1,019,484
	2.0	637,178	318,589
	3.0	223,013	111,507

Table 2. Sample Size Calculations for the Weighted Cox Regression Using the Internal Comparator Cohort Design

Matching ratio		Number of controls	Number of ABRYSVO	
(controls:	IRR	needed in each	vaccinated individuals	
ABRYSVO		comparator cohort (N)	needed (N)	
vaccinated)		_		

Abbreviations: IRR, incidence rate ratio.

Notes:

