9.7. Data Analysis

Detailed methodology for summary and statistical analyses of data collected in this study will be documented in an SAP, which will be dated, filed, maintained by the sponsor, and submitted to the Agency. The SAP may modify the plans outlined in the protocol; any major modifications of primary endpoint definitions or their analyses will be reflected in a protocol amendment.

All analyses will be conducted separately among individuals at least 60 years of age and among individuals 18-59 years of age. Pooled analyses among adults 18 years of age and older may be conducted using combined individual-level data from both age groups. Baseline characteristics will be descriptively compared and heterogeneity in the estimated incidence rates of atrial fibrillation among the 18-59 years old and 60 years and older age groups will be assessed using a two-population test (eg, Fisher's exact test or Z-test). If significant heterogeneity is observed with respect to patient characteristics (other than age) and incidence rate estimates, then no pooled analyses will be conducted. Otherwise, if heterogeneity is not observed and characteristics are considered to be sufficiently similar, then individual-level data from both age groups will be combined, and the descriptive analyses of characteristics and outcomes will be conducted using the combined dataset. If sample size is sufficient to allow comparative cohort analyses to be performed separately among individuals 18-59 years of age and individuals 60 years and older, then comparative analyses will also be performed in the pooled population. Further details will be provided in the SAP.

Data analyses will be conducted using SAS Enterprise Guide version 7.1 (SAS Institute Inc., Cary, NC) or R Version 3.5.3 or its latest version (R Core Team, Vienna, Austria).

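### Ages 18-59, days 0-3: the 1.5-fold sample size exceeds the plan's own eligible population, 2-fold needs very high uptake, and the pooled comparison is tied to this group

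*Protocol*

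**What the plan says.** Protocol 9.5.1 derives the eligible younger population from nine million enrollees and concludes that "an estimated 330,000 to 868,000 VHA enrollees aged 18 to 59 may be eligible for inclusion in the study". For the internal comparator design it then states that "a sample size of 286,730 and 892,049 individuals vaccinated with ABRYSVO is needed to detect a 2-fold and 1.5-fold" increase, at one-sided 5%, "a power of 80%, and a risk interval of 4 days corresponding to the 0-3 day risk interval". The inputs are a "background rate of 4.4 per 1,000 person-years for incident atrial fibrillation reported for males 45-54 years of age", and "assuming the same matching rate of controls to ABRYSVO vaccinated individuals (ie, 4:1 ratio" as for the older group. Table 2 adds 1,146,920 controls for the 2-fold row and 3,568,194 for the 1.5-fold row, per comparator cohort. Table 3 asks for 294,458 and 989,381 vaccinees for the SCRI at days 0-3. The Abstract repeats the comparator-cohort vaccinee numbers.

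Section 9.2.1 requires controls aged 18-59 to carry a risk condition for severe RSV, so they come from the same at-risk population as the estimate above.

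Two rules rest on sample size. Section 9.5.1 says of the secondary objective that "comparative analyses will only be conducted when a sufficient number of atrial fibrillation events have been observed" for adequate power, without naming the ratio. Section 9.7 says that "heterogeneity in the estimated incidence rates of atrial fibrillation among the 18-59 years old and 60 years and older age groups will be assessed" before pooling. It introduces the pooled comparison with the condition "If sample size is sufficient to allow comparative cohort analyses to be performed separately among individuals 18-59 years of age" and among those 60 and older.

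**The concern.** A requirement larger than the population from which it must be drawn describes a study that cannot exist. A reader of the Abstract or Table 2 has no warning of this, because the required numbers and the eligible numbers are never set against each other and no uptake forecast is given.

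The two rules carry the problem further. If adequate power means 1.5-fold at days 0-3, the 18-59 comparison can never be run. If it means 3-fold, it might be. The plan leaves this open, so the decision to compute a hazard ratio could be made after event counts are known. The pooled comparison, which serves the secondary objective worded for all adults, then waits on the group least able to supply events. The pooling screen also looks at whether AF incidence is alike in the two age groups. That is not the condition for pooling a hazard ratio: baseline hazards may differ freely between strata, and what matters is whether the effect of vaccination is similar.

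**Working it through.** **Inputs (Protocol 9.5.1 and Tables 2-3).** One-sided α = 0.05, power 80%, 4-day interval, 4 controls per vaccinee; background rates 4.4 (18-59) and 33.9 (60+) per 1,000 person-years.

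**1. Reproduce the eligible population.** (9,000,000 − 1,000,000) × 0.44 × 0.85 = 2,992,000. Multiplied by 11% this is 329,120, and by 29% it is 867,680, matching 330,000 to 868,000. The upper end is generous, since it applies the 50-64 prevalence to everyone aged 18-59.

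**2. Reproduce Table 2.** With p0 = rate × 4/365 and k controls per vaccinee,

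n = (1.645 + 0.842)² × (IRR + 1/k) / [p0 × (IRR − 1)²], where the squared term is 6.183.

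- 60+, IRR 2: p0 = 0.00037151, n = 6.183 × 2.25 / 0.00037151 ≈ 37,444 (stated 37,444).
- 18-59, IRR 2: p0 = 0.00004822, n ≈ 288,490 (stated 286,730).
- 18-59, IRR 1.5: n ≈ 897,525 (stated 892,049).

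The 18-59 rows differ by a constant 0.6%, consistent with an unrounded rate near 4.43. The table is not miscalculated.

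**3. Set the required numbers against the eligible population (days 0-3, 18-59).**

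| Target | Vaccinees needed | Share of 868,000 | Share of 330,000 |
|---|---|---|---|
| 1.5-fold, cohort | 892,049 | 103% | 270% |
| 1.5-fold, SCRI | 989,381 | 114% | 300% |
| 2-fold, cohort | 286,730 | 33% | 87% |
| 2-fold, SCRI | 294,458 | 34% | 89% |
| 3-fold, cohort | 103,542 | 12% | 31% |

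Controls at 4:1 for 2-fold: 1,146,920 / 868,000 = 132%, before any vaccinee is counted. Total people if all are distinct: 286,730 + 1,146,920 = 1,433,650 (165% of 868,000). At 2:1: 318,589 + 637,178 = 955,767 (110%). For 3-fold at 4:1: 103,542 + 414,166 = 517,708, which is 60% of 868,000 but 157% of 330,000.

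**4. Detectable ratio at assumed uptake.** The protocol gives no uptake figure, so 20% and 10% are assumptions. Solving the formula in step 2 for the ratio, at 4:1:

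- 20%: 66,000 to 173,600 vaccinees; smallest detectable ratio 3.8 to 2.4.
- 10%: 33,000 to 86,800 vaccinees; ratio 5.9 to 3.3, with n × p0 = 1.6 to 4.2 background events expected among vaccinees.

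**5. The longer interval.** Table 3 for days 0-30 needs 47,873 vaccinees for a ratio of 2 (5.5-14.5% of the population) and 164,897 for 1.5 (19-50%). Scaling Table 2 by 4/31 gives about 37,000 vaccinees and 148,000 controls for 2-fold.

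**6. The pooling screen.** Planning rates differ by 33.9 / 4.4 = 7.7. Counts were simulated as Poisson at those rates, with 116,493 vaccinees aged 60+ (the 1.5-fold number, about 43 expected events), and compared by a two-sided exact conditional test at 5%. Equality is rejected about 78% of the time with an assumed 20,000 vaccinees aged 18-59, about 96-98% with 33,000, and nearly always with 103,542. On the planning rates, the incidence part of the screen is close to decided in advance.

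**The case against.** The case for the plan is substantial. The text gives numbers that are needed; it does not promise that the 18-59 group will reach them. Section 9.5 says the size achieved depends on how many are vaccinated, and 9.5.1 provides for uptake monitoring and a contingency discussion with the FDA. That stands, but no contingency brings a requirement of 892,049 within an eligible population of at most 868,000.

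A reader might infer that 2-fold is impossible too. The documents do not support this. Both 2-fold vaccinee numbers are below even 330,000, and the SCRI needs no separate controls. Controls may later enter the vaccinated cohort (9.1.1, 9.2.1), and nothing excludes a lower matching ratio. With distinct people and 868,000 eligible, about 85% power for 2-fold is attainable at 58% uptake and roughly 0.7 controls per vaccinee; with 330,000 the best is about 50%.

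A reader might also infer that the 18-59 and pooled comparisons are ruled out. That does not follow either. Adequate power is tied to no ratio, 9.5.1 mentions a risk ratio above 3 as meaningful, and 3-fold may be reachable. The pooled rule is worded as a condition under which the comparison will be done, not as an explicit prohibition otherwise. The explicit bar on pooling requires heterogeneity in patient characteristics and in incidence together, although the sentence after it is looser. Pooling is optional, and details are left to the SAP. So the rule is ambiguous and badly aimed rather than certain to block.

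Finally, few events would not go wholly unreported: incidence rates with 95% intervals (9.7.2.1) are produced whatever the event count. Only the hazard ratio is at risk.

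**Conclusion.** The point holds for ages 18-59 at days 0-3, as a feasibility contradiction rather than an arithmetic slip. The 1.5-fold target is unreachable on the plan's own figures in both designs. Two-fold is arithmetically possible but needs a third to nearly nine-tenths of all eligible enrollees to receive one brand, and at 4:1 it needs controls to be reused. Three-fold and the 0-30 day interval are much less demanding.

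The ratio behind adequate power is unstated, and the pooling rule depends on the wrong quantity and on the weakest group. Required shares rest only on figures in the protocol; detectable ratios and rejection probabilities rest also on the assumed uptake and group sizes shown.

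Severity is should-fix. The primary objective is incidence estimation and is untouched. The 60+ comparison needs 37,444 vaccinees for 2-fold and 116,493 for 1.5-fold out of about 3.8 million eligible (1.0% and 3.1%).

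**What to change.** 1. In the Abstract, 9.5.1 and Tables 2-3, state that 1.5-fold at days 0-3 is not attainable for ages 18-59. State the uptake and the control reuse that 2-fold requires. Add the detectable ratio at feasible numbers, with the uptake assumption named, such as those in step 4 of the working.
2. Fix the ratio that defines a sufficient sample in 9.5.1 and 9.7. Alternatively, report the hazard ratio with its confidence interval whatever the event count, labelled imprecise when events are few.
3. In 9.7, replace the incidence-equality screen and the separate-sufficiency condition by a weighted Cox model stratified by age group, with weights fitted within age group. Use an ABRYSVO-by-age-group interaction as the heterogeneity check.

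Cost: protocol and SAP wording and one extra model. The published 18-59 figures become less favourable. No extra patients are needed.
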